## STUDY SUMMARY

It may be useful to include a brief synopsis of the study for quick reference. Complete information and, if required, add additional rows.

Study Title	ReHabGame: A Markerless, Game-Based Rehabilitation program
Internal ref. no. (or short title)	ReHabGame

Study Design	
Parallel, two-cohort (Neurological, MSK), two-arm RCT
 
Arms (within each cohort):
 
 
1. Usual Care only
 
2. Combined ReHabGame + Usual Care
 

Study Participants	
 
• Age 18+ years
 
• Ability to follow simple instructions and give consent
 
• No severe cognitive impairment (MoCA <math>\geq 22</math>)
 
• Stable medical condition (no recent cardiovascular event)
 

Planned Size of Sample (if applicable)	
Planned Sample Size per cohort (Neurological or MSK):
 
23 participants per arm: 2 arms = 46 participants
 
Total across both cohorts:
 
46 (Neurological) + 46 (MSK) = 92 participants
 
Allowing for ~20% attrition,

Follow up duration (if applicable)	4-week post-intervention follow-up (Week 12)
Planned Study Period	
Participants to be randomised to:
 
 
1. ReHabGame: 30–45 min sessions, 2x/week for 6–8 weeks
 
2. Usual care: standard physio sessions, 2x/week for 6–8 weeks
 

Research Question/Aim(s)	
Primary Objectives: feasibility endpoints
 
(Combined = ReHabGame + usual care; Control = usual care only)
 
 
• Neurological cohort:
 

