### 3. Intervention Sessions (Weeks 1–8): Questionnaire at week 2, 4, 8 (**via the above Link**)

- Combined arm only; 2x/week, Weeks 1–8

Usual care only:

- o 30–45 min therapist-led physiotherapy per session
- o 2 sessions/week for 6–8 weeks (standardised protocol)
- **Combined care- Usual-care + ReHabGame:**
  - o 30–45 min Kinect-guided exercises per session.
  - o Real-time difficulty adaptation; metrics auto-logged.
  - o Both modalities, each 2x/week (on separate days or back-to-back).
  - o Each session is logged in the PDF format.

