### 1. Descriptive / Feasibility Metrics

- **Recruitment rate:**
  - Number screened, number eligible, number randomised (%)
- **Retention & adherence:**
  - Proportion completing Week 8 assessment in each arm (%)
  - Mean ( $\pm SD$ ) number of sessions attended per arm
- **Data completeness:**
  - Proportion of missing outcome data at each timepoint

These will be reported as counts, percentages, and 95% confidence intervals.

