## Secondary Research Questions

Within each cohort, how do the two arms compare on:

- **Functional independence:** Barthel Index (Neurological) or DASH (MSK)
- **Engagement & usability:** System Usability Scale (SUS) scores and engagement survey ratings at Weeks 4, 8, 12
- **Session adherence:** Number and proportion of prescribed sessions completed
- **Motion-tracking performance:** Changes in Kinect-derived metrics (range of motion, smoothness, accuracy)
- **Pain & ROM (MSK only):** Pain VAS and goniometric ROM

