## 5 STUDY DESIGN and METHODS of DATA COLLECTION AND DATA ANALYSIS

Type: Parallel, two-cohort (Neurological vs MSK), two-arm randomized controlled trial

- Arms (within each cohort):
  1. Usual-care physiotherapy only
  2. Combined ReHabGame + usual-care

Allocation: 1:1 randomisation, stratified by baseline severity (high vs low) within each cohort

- Blinding:
  - Outcome assessors blinded to group assignment

- Participants & therapists unblinded (interventions are overt)
- Duration: 6–8 weeks of intervention (2 sessions/week) + 4-week follow-up
- Sample size: 23 per arm per cohort (46 per cohort; 92 total), allowing ≈20% attrition.

Domain	Instrument & Timing
Demographics & History	Structured questionnaire at Week 0 (age, sex, diagnosis, time since onset/surgery, comorbidities)
Primary Outcomes	- Neurological: Fugl–Meyer Assessment (upper extremity) at Weeks 0, 8- MSK: SPADI at Weeks 0, 8
Secondary Outcomes	- Neurological: Barthel Index at Weeks 0, 8- MSK: DASH, pain VAS, goniometric ROM at Weeks 0, 8
Interim Metrics	At Week 4 for all: SUS, engagement survey, adverse-event checklist, quick FMA-UE subset (neuro) or SPADI re-test (MSK), Kinect snapshot metrics
Follow-up Metrics	At Week 12: SUS, engagement survey, adverse-event update, optional brief functional check
Motion-Tracking Data	Automatically logged each session via Kinect: range of motion, smoothness (jerk), repetition count, completion time, accuracy
Session Adherence	PDF session log (date, duration, pain VAS, issues) maintained by participant; automatically generated session report PDFs summarising movement metrics
Qualitative Feedback	Semi-structured interview or written feedback at end of Week 8 (usability, barriers, facilitators, motivation)
Safety Monitoring	Adverse events recorded at every session and via AE checklist at Weeks 4, 8, 12; severity and relatedness noted

All analyses conducted separately within each cohort on an intention-to-treat basis,  $\alpha = 0.05$  two-sided.

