### 1. Feasibility & Descriptive Statistics

- Recruitment, retention, and adherence rates: counts (%) with 95% CIs
- Session completion: mean  $\pm$  SD sessions attended per arm
- Data completeness: proportion of non-missing data per outcome

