### 3. Secondary & Repeated-Measures Analyses

- **Continuous outcomes** (Barthel, DASH, Pain VAS, ROM, SUS, engagement scores):
  - ANCOVA at Week 8 as above
  - **Mixed-effects linear models** for repeated measures (Weeks 0, 4, 8) with fixed effects for time, arm, and timexarm; random intercepts for participants
- **Categorical safety outcomes:** AE counts compared via  $\chi^2$  or Fisher's exact tests

4. **Motion-Tracking Metrics**
  - o Compare mean ROM, smoothness, completion time, and accuracy at Weeks 4 and 8 using ANCOVA, adjusting for baseline Kinect metrics
5. **Exploratory Analyses**
  - o **Cost/resource use:** descriptive comparison of therapist time and equipment costs per participant (t-tests or nonparametric equivalents)
  - o **Qualitative data:** thematic analysis of interviews to identify barriers/facilitators; representative quotes to illustrate key themes
6. **Missing Data**
  - o **< 5% missing:** complete-case analysis
  - o **≥ 5% missing:** multiple imputation by chained equations (20 datasets) including baseline covariates and outcomes
  - o **Sensitivity:** per-protocol analysis (≥ 75% sessions attended)
7. **Safety Review**
  - o AE rates summarised by arm; reviewed by an independent Data Monitoring Committee at midpoint (after ~50% complete)

All statistical programming and reporting will be done in R ( $\geq 4.0$ ), with scripts version-controlled for reproducibility.

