## Staff Training

- Staff at both sites will receive a brief orientation on ReHabGame's operation, the motion-tracking sensors, and participant safety protocols.
- Any site-specific health and safety training required by hospital policy (e.g., manual handling, infection control) must be completed by the research team.

1. Identification & Recruitment
  - At each site, clinical teams (physiotherapists, occupational therapists, rehab consultants) will introduce the study to eligible patients and, if they express interest, refer them to the research team for formal screening.
  - Potential participants will receive an information sheet and have an opportunity to ask questions before providing written informed consent.
2. Baseline Assessments
  - Participants will undergo baseline clinical evaluations (e.g., Fugl-Meyer Assessment), and relevant questionnaires.
  - These may take place in a private clinic room or dedicated rehabilitation space.
3. ReHabGame Intervention
  - Participants will use ReHabGame in designated therapy areas equipped with the Kinect hardware.
  - Session frequency and duration will follow the study protocol (e.g., 1–2 sessions per week over 6–8 weeks).
  - Research staff or designated clinical staff will supervise sessions, ensuring correct usage and participant safety.
4. Data Collection
  - Quantitative: System logs (range of motion, frequency of play), standardized clinical scales (pre-/post-intervention).
  - Qualitative: Questionnaire to gather feedback on user experience and feasibility.
5. Follow-Up Assessments
  - Post-intervention evaluations will be conducted to assess changes in upper-limb function and gather final feedback.
  - Data will be entered into secure, password-protected electronic databases, ensuring confidentiality and compliance with data protection laws.

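### The protocol contradicts itself on arms, session frequency and duration, so the prescribed number of sessions behind the attendance summary and the 75% per-protocol rule is not fixed

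*Protocol*

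**What the plan says.** **Arms.** The design row of the Study Summary, and almost all of the protocol, compares usual care alone with ReHabGame added to usual care. The Planned Study Period row of the same table randomises to ReHabGame or to usual care ("standard physio sessions, 2x/week for 6–8 weeks") and does not mention the combination.

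**Frequency.** Section 5 gives "Duration: 6–8 weeks of intervention (2 sessions/week) + 4-week follow-up", without saying whether this is per modality or in total; the Study Flow Chart does the same. The Intervention Sessions item of the study timeline gives the combined arm "Both modalities, each 2x/week (on separate days or back-to-back"). Section 6 (Staff Training, item 3) says of the game: "Session frequency and duration will follow the study protocol (e.g., 1–2 sessions per week over 6–8 weeks").

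**Duration.** The Study Summary, flow chart, Section 5 and Section 6 give a range of six to eight weeks. The Intervention Sessions item also places the combined arm's sessions in Weeks 1–8, and Appendix 2 has the Kinect exercises running twice a week for eight weeks. No rule says who receives six weeks and who receives eight.

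**Use in the analysis.** The Planned Statistical Analyses summarise the mean "number of sessions attended per arm", and Section 5 likewise reports mean and "SD sessions attended per arm". The secondary research questions ask for "Number and proportion of prescribed sessions completed". The sensitivity analysis in Section 5 is given as "per-protocol analysis (≥ 75% sessions attended"), with neither modality nor denominator named.

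**Timing labels.** The Week 8 visit is called the end of the intervention. The Study Summary places Week 12 four weeks after it.

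**The concern.** Adherence is a main output of this pilot. Section 7.2.1 justifies the sample size partly by the precision with which adherence rates can be estimated. A proportion of prescribed sessions needs a prescribed number, and the protocol supplies several. If the arms are scheduled different numbers of sessions, a raw mean count mostly reflects the schedule and says little about adherence.

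The same gap affects the per-protocol set: who belongs to it depends on which section is followed and on whether the two modalities are counted together. Each cohort is recruited at a single site, so two sites reading the schedule differently would give the two cohorts different doses. The time from the last session to the Week 8 and Week 12 assessments would also vary between participants, contrary to the labels on those visits.

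**Working it through.** The protocol states no total number of sessions, so there is no figure to reproduce. The check is what each section implies.

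**Inputs.** Usual care: 2 sessions a week for 6–8 weeks (Intervention Sessions). Game: 2 a week (Intervention Sessions, Appendix 2) or 1–2 a week (Section 6). Alternative reading: 2 a week in total in either arm (Section 5, flow chart). Threshold: 75%.

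**Scheduled sessions** = sessions per week × weeks, with the same course length in both arms. **Minimum to qualify** = 0.75 × scheduled, rounded up, counting all sessions together.

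| Reading | Usual care | Combined | Ratio | Minimum, usual care | Minimum, combined |
|---|---|---|---|---|---|
| Each modality 2 a week | 12–16 | 24–32 | 2.0 | 9–12 | 18–24 |
| Usual care 2, game 1 a week | 12–16 | 18–24 | 1.5 | 9–12 | 14–18 |
| 2 a week in total | 12–16 | 12–16 | 1.0 | 9–12 | 9–12 |

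**Exposure to the game under an overall 75% rule.** Take a combined-arm participant who attends every usual-care session.
- Each modality 2 a week, 8 weeks: 24 − 16 = 8 of 16 game sessions are enough, since (16 + 8)/32 = 75%.
- Each modality 2 a week, 6 weeks: 18 − 12 = 6 of 12 are enough.
- Game once a week: 14 − 12 = 2 of 6 (6 weeks) or 18 − 16 = 2 of 8 (8 weeks) are enough.
- Usual care only, no game: 16/32 = 50%, which does not qualify.

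**Effect of the unfixed course length in usual care.** Nine sessions are 9/12 = 75% of a six-week course (in) but 9/16 = 56% of an eight-week course (out). A participant who completes six weeks in full has 12/12 = 100% or 12/16 = 75%, depending on the denominator.

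**Timing** = assessment week − last treatment week.
- Week 8: 8 − 6 = 2 weeks, or 8 − 8 = 0 weeks, after the last session.
- Week 12: 12 − 6 = 6 weeks, or 12 − 8 = 4 weeks, after the last session.

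The four-week label therefore fits only an eight-week course. If game sessions always run to Week 8 while usual care may stop from Week 6, the gap before Week 8 can also differ by arm.

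**The case against.** Several stronger readings are tempting, and the documents do not support them.

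- *The 75% rule treats equal adherence unequally.* It does not. In the example the combined participant misses 8 of 32 sessions (25%). A control who misses 25% attends 12 of 16 = 75% and is included. A control who misses the same number, 8 of 16, attends 50% and is excluded. Only the number missed is equal.
- *The protocol pools the modalities.* It is silent. Pooling is one reading, and a statistical analysis plan, not shown here, may define the set by component. That silence alone would be no finding.
- *Adherence is planned only as a raw count.* The secondary research questions name a proportion of prescribed sessions, and Section 5 also lists adherence rates as percentages with confidence intervals. The mean count is descriptive and no test is attached to it.
- *The combined arm receives double the sessions by design.* Only the Intervention Sessions item clearly says so. The Section 6 frequency is given as an example and defers to the protocol.
- *The extra contact time invalidates the comparison.* Sections 1 and 4 ask for the benefit of adding ReHabGame to usual care. More sessions are inherent in an add-on arm, and therapist time is already compared by arm.
- *The primary analysis is compromised.* Week 8 is a fixed time from baseline in both arms, so the intention-to-treat ANCOVA remains valid. What varies is the dose received and up to two weeks in time since the last session.

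These points narrow the concern but do not remove it. A proportion of prescribed sessions is only as well defined as the prescription, and a later analysis plan cannot cure contradictory instructions that the sites must follow.

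**Conclusion.** The point holds in a limited form. The contradictions on arms, frequency and duration are in the text. They leave the scheduled number in the combined arm anywhere from 12 to 32 sessions, and its ratio to usual care at 1.0, 1.5 or 2.0 for equal course lengths. Unless the ratio is 1.0, the mean number of sessions attended cannot be compared between arms as a measure of adherence. If the 75% rule is applied to all sessions together, which is an assumption, it can admit someone who missed half the game sessions when both modalities run twice a week, and more than half when the game runs once a week. The Week 8 and Week 12 labels are right only for an eight-week course. The damage is to the feasibility measures and one sensitivity analysis, not to the primary analysis.

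**What to change.** 1. The sponsor must reconcile the Study Summary (both rows), Study Flow Chart, Intervention Sessions item, Section 5, Section 6 (Staff Training, item 3) and Appendix 2 on arms, frequency per modality and duration. Which schedule applies is the sponsor's decision. The Week 8 and Week 12 labels should then be made to agree with it.
2. Report attendance by modality as a percentage of scheduled sessions, in line with the secondary research question. Compare the arms on usual-care attendance only, and report ReHabGame attendance for the combined arm only.
3. Define the per-protocol set as at least 75% of each allocated component.

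**Cost.** The changes are to wording. The per-protocol set in the combined arm will be smaller; the documents give no figure from which to estimate by how much. Session type must be recorded at every session. At present the QR scan that captures it is optional (Section 7.3.2), and the fields listed for the participant's session log in Section 5 do not include it.

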## Data Handling Procedures

- De-Identification: **Personal identifiers will be removed or replaced with participant IDs in all datasets.**
- Storage and Transfer:
  - o Electronic files (e.g., transcripts, quantitative spreadsheets) will be stored on secure, password-protected servers.
  - o Paper records (e.g., signed consent forms) will be kept in locked filing cabinets in a restricted-access area.
- **Access:** Only authorized research staff who have signed confidentiality agreements will have access to identifiable information.
- **Archiving:** At the end of the study, de-identified data will be archived according to institutional and regulatory guidelines, typically for up to three years or as required by policy.

By combining quantitative assessments with in-depth qualitative insights, this study design and data analysis plan will provide a well-rounded understanding of how ReHabGame affects upper-limb rehabilitation outcomes and user experiences.

## 6 STUDY SETTING

### Access to Expertise

- On-site neurologists, physiotherapists, occupational therapists, and rehabilitation nurses can provide immediate clinical support if participants have any medical concerns or adverse events.
- The clinical teams' involvement ensures high-quality, clinically relevant data collection and safe implementation of the study protocol.

This is a multi-centre study involving:

1. Mid and South Essex NHS Foundation Trust Site A  
Southend University Hospital, [name]
2. Physio4You – NeuroPhysio Team - Site B

Both sites will follow the same overall protocol, but each location will manage its own recruitment, screening, and data collection processes.

**Site A: Southend General Hospital (NHS)**

**Cohort:** MSK only.

**Recruitment:** Patients with eligible musculoskeletal shoulder conditions will be identified from outpatient orthopaedic and physiotherapy clinics.

All interventions will be delivered on-site by NHS physiotherapists trained in the study protocol.

### **Site B: Physio4You (Private Neuro-Physiotherapy Centre)**

**Cohort:** Neurological only (stroke, traumatic brain injury, multiple sclerosis).

#### **Clinical Oversight:**

The study at this site will be managed under the supervision of [name], Director and NeuroPhysio Clinical Lead Physiotherapist at Physio4You.

#### **Usual Care Referral Pathway:**

Neurological patients attending Physio4You are typically referred through one of the following routes:

- NHS consultants or GPs following hospital discharge.
- Community neurological rehabilitation teams.
- Self-referral by patients already diagnosed and managed under the care of an NHS or private neurologist.

Once accepted into Physio4You's care, each patient's overall clinical oversight remains with their referring physician or consultant. Physio4You clinicians provide physiotherapy

input in line with the referring clinician's management plan and within the scope of usual care.

### **Role in the Study:**

Physio4You will provide a controlled clinical environment for:

- Delivery of the ReHabGame intervention to neurological participants.
- Collection of study outcome measures.
- Monitoring participant safety and session adherence.

All intervention sessions will take place within the Physio4You clinic only.

Although Physio4You routinely offers domiciliary services, no home-based or community sessions are included in this study protocol.

### Recruitment Pathway & Access to Records:

- Recruitment will be conducted only by clinicians with legitimate access to patient records as part of their usual clinical role (e.g., treating physiotherapists or rehabilitation consultants).
- These clinicians will act as clinical gatekeepers, screening caseloads and medical records for potentially eligible participants and providing study information to suitable patients.
- If patients agree, the study will be conducted at the Physio4You site under [name] direct supervision.
- Research staff or assistants will not access medical records prior to consent. Their role begins only once a patient has been referred and has provided written consent to participate.

### **Site Readiness:**

[name] has been trained in the use of the ReHabGame software and hardware. A dedicated computer and Kinect sensor have been provided, with all setup requirements completed. The trial of neurological assessments and intervention sessions will therefore be conducted under his direct supervision at the Hertfordshire site.

Refer interested patients to the research team.

Research staff/research assistants will not directly access medical records prior to consent. Their role begins only once a patient has been referred and has provided consent to be contacted.

This ensures that all pre-consent record reviews are compliant with NHS and GDPR requirements, limited to those with a direct clinical care relationship.

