#### 5. End-Of-Intervention Assessment (Week 8)

- Full repeat of baseline tests supervised by a clinician the above link can be used “*ReHabGame: Assessments at Week 4 (interim), Week 8 (end), Week 12 (follow-up)*”.
- Patients receive session report PDF summarising all movement metrics over the course of the study.

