ReHabGame is a markerless, game-based rehabilitation system that integrates Kinect-derived motion tracking with a bespoke adaptive algorithm to tailor exercise difficulty in real time. In this study we designed a two-cohort, two-arm RCT comparing **Combined ReHabGame + usual care** versus **usual care alone**, in both neurological and MSK cohorts. By stratifying participants and blinding outcome assessors, this study will determine the added value of ReHabGame when combined with usual care, characterize feasibility metrics (recruitment, retention, adherence), and generate robust data on functional gains, pain modulation, and motion-tracking validity.

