##### 2. MSK cohort:

- Does Combined ReHabGame + usual care produce greater improvement in shoulder pain and function (SPADI, baseline→Week 8) compared to usual-care alone?

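### Assessor blinding is claimed without qualification, but one lead supervises both neurological assessments and game sessions, no blinded rater is described after baseline, and SPADI falls outside the blind

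*Protocol*

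**What the plan says.** **The claim.** The Background relies on assessor blinding: "By stratifying participants and blinding outcome assessors". The blinding list in Section 5 repeats it, "Outcome assessors blinded to group assignment", and adds "Participants & therapists unblinded (interventions are overt".

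**Neurological site.** The Site Readiness text in Section 6 states: "The trial of neurological assessments and intervention sessions will therefore be conducted under his direct supervision". The same paragraph says this lead has been trained on the ReHabGame software and hardware. The Clinical Oversight text identifies the role as director and clinical lead physiotherapist of the site. The site both delivers the intervention and collects the outcome measures (Section 6, Role in the Study).

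**Week 8 visit.** Item 5 of Study Timeline and Procedures describes the tests as "Full repeat of baseline tests supervised by a clinician" and then lists: "Patients receive session report PDF summarising all movement metrics over the course of the study". The table in Section 5 places the usability interview or written feedback at the end of Week 8.

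**MSK cohort.** The primary question in Section 4.1 is "Does Combined ReHabGame + usual care produce greater improvement in shoulder pain and function", measured by SPADI from baseline to Week 8.

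**The concern.** FMA-UE is scored by an observer, so it is the primary outcome that assessor blinding can protect. For that cohort, the conduct text puts a person who must know allocation in direct charge of the assessments. It also sets no condition that the Week 8 rater be blinded or independent of treatment. For SPADI, blinding an assessor does nothing, because the rating comes from a participant who knows the arm.

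The feasibility label does not remove the problem. The protocol plans an adjusted mean difference with a confidence interval and p-value for each primary outcome (Planned Statistical Analyses, item 2). It aims to determine added benefit (Section 4), and it expects evidence for or against routine use (Section 4.2). Knowledge of the arm would most plausibly favour the Combined arm. Scores collected unblinded cannot be repaired at analysis.

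**Working it through.** The protocol states no figure on this point, so the check is mainly a comparison of its own statements.

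1. **Does the neurological lead know allocation?** Item 3 of Study Timeline and Procedures gives Kinect-guided sessions to the Combined arm only. Site Readiness has the lead directly supervise intervention sessions. Whoever does that learns who is in the Combined arm. This is an inference, but a short one.

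2. **Does the lead have a role in assessment?** Yes, by the same sentence in Site Readiness. The stated role is supervision, not scoring.

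3. **Is another rater described?** Item 1 of Study Timeline and Procedures mentions an assessor for the baseline test. It does not call that person blinded, and randomisation follows the test. From Week 4 onward no rater is described. Week 8 mentions only a supervising clinician, and Section 5 declares therapists unblinded.

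4. **Does anything at the Week 8 visit reveal the arm?** Movement metrics are logged at each Kinect session (Section 5 table), and those sessions belong to the Combined arm. A report covering the whole study therefore exists, in practice, only for game users. The usability interview falls at the same time point. No order is set, and no separation of staff.

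5. **What does assessor blinding cover in the MSK cohort?** Section 5 lists SPADI, DASH, pain VAS and goniometric ROM. The first three are by their nature participant ratings, and participants are unblinded. ROM is the observer-rated measure.

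**Illustration of scale (assumed bias).** Inputs: at least 18 completers per arm (Section 7.2.1) and two-sided α = 0.05 (Planned Statistical Analyses). The protocol gives no SD, so bias b is in SD units. The range 0.2 to 0.3 is an assumption.

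- Unadjusted standard error: √(2/18) = 0.333 SD.
- Bias relative to it: 0.2/0.333 = 60%; 0.3/0.333 = 90%.
- False-positive rate with no true effect, by normal approximation: Φ(b/SE − 1.96) + Φ(−b/SE − 1.96).

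| Assumed bias (SD) | 18 per arm | 23 per arm |
|---|---|---|
| 0 | 5.0% | 5.0% |
| 0.1 | 6.0% | 6.3% |
| 0.2 | 9.2% | 10.4% |
| 0.3 | 14.7% | 17.4% |

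The rates rise with sample size because the bias stays fixed while the standard error shrinks. The table is not evidence that any bias exists.

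**The case against.** **Supervising is not scoring.** The Site Readiness sentence can be read as general site oversight, with a separate blinded rater working under it. That reading is compatible with Section 5. It stands to this extent: a reader might infer that the lead scores FMA-UE, or that the blind is already broken, and the documents show neither. But direct supervision of the assessments by someone who knows the arm is itself at odds with an unqualified blinding claim, so more than detail is missing.

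**No stake is shown.** A reader might infer that the lead has an interest in the system's success. The protocol records only the site role and the training.

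**Week 4 items do not reveal the arm by their presence.** The Section 5 table lists the usability scale, engagement survey and "quick FMA-UE subset (neuro) or SPADI re-test (MSK), Kinect snapshot metrics" for everyone. Only what a participant says could reveal the arm. This stands, and the point about arm-revealing items is therefore confined to Week 8.

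**The report's recipients are not stated by arm.** Item 5 of the timeline refers to patients generally, Section 7 lists session PDFs as a general retention measure, and Section 5 compares Kinect metrics between arms. Control participants might thus have snapshot data. They would still have no game-session record to summarise. Nor does any text route the report or interview through the outcome assessor; equally, none keeps them apart.

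**Participant unblinding is disclosed and unavoidable.** That is correct and is no fault. The protocol also does not say who completes SPADI; self-completion follows from the type of instrument. What remains is that the blinding claim carries no statement of which outcomes it covers.

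**This is a pilot.** Section 7.2.1 says the sample is not powered for definitive testing. That lowers the severity but does not settle who rates the outcome.

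**Conclusion.** The concern holds as a conflict within the protocol, to be corrected as a should-fix. Section 5 and the Background claim blinded assessment. The neurological site text and the Week 8 procedures allow a person who knows allocation to oversee an observer-scored primary outcome, and no blinded rater is described after baseline. In the MSK cohort the claim does not reach the primary outcome.

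The conclusion rests on two inferences: that supervising Combined-only sessions reveals allocation, and that SPADI is self-rated. The size of any bias is unknown. The 60% to 90% of a standard error shown above depends wholly on the assumed 0.2 to 0.3 SD. A reader might infer that both primary results will be biased by that amount; the documents give no support for any particular amount.

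**What to change.** 1. Reconcile Site Readiness (Section 6) and item 5 of Study Timeline and Procedures with Section 5. State that the Week 8 FMA-UE, the Week 4 FMA-UE subset and goniometric ROM are scored by the blinded assessor whom Section 5 already promises. State also that nobody who delivers or supervises a participant's sessions scores that participant or supervises the scoring.
2. At Week 8, complete and lock FMA-UE and ROM before the session report and the usability interview, and have someone else handle those two items.
3. In the Background and Section 5, limit the blinding claim to observer-rated measures. State that SPADI, DASH and pain VAS are unblinded if self-completed.

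Recording the assessor's guess of allocation, and reading SPADI beside ROM, are optional additions.

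**Cost.** Protocol wording and a set order at one visit. The neurological site must keep assessor and supervisor rotas apart; whether its present staff can do so is not stated. The MSK claim becomes weaker, but accurate.
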